## 6.6 SUBGROUP ANALYSES

Key safety and/or efficacy parameters will also be analyzed by the following subgroups:

- ECOG Performance status: 0–1 vs. 2
- Presence of CNS metastases at baseline: yes vs. no
- Renal impairment at study entry: yes vs. no
- Patient requiring dialysis: yes vs. no
- HIV status: negative vs. positive
- History of autoimmune disease: yes vs. no
- Progression on, or within 12 months of, prior platinum-based treatment: yes vs. no
- Concomitant steroid treatment ongoing at baseline: yes vs. no
- History of non-urothelial urinary tract carcinoma histology: yes vs. no
- Previous lines of cancer therapy (1 vs. 2 vs. 3)
- Age-adjusted Charlson comorbidity index (AACI):  $\leq 11$  vs.  $> 11$
- PD-L1 expression: low vs. high (cut-offs to be defined)
- Region (grouping countries into regions will be specified in the Statistical Analysis Plan)

All subgroup analyses will be based on the same methods as overall analyses of the primary and secondary variables. In addition, graphical displays such as forest plots will be used to descriptively visualize the homogeneity of key safety and efficacy parameters (proportions and 95% CI, or KM medians and corresponding 95% CI, as applicable will be displayed) across different levels of the pre-specified subgroup variables.

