 - PD-L1 expression by IHC class (IC0 to IC3)
 - PD-L1 expression: IC0/1 or IC2/3

Renal dialysis reported at baseline is defined as 'No' for all patients included with protocol version < 5 (regardless if any or no dialysis reported or no information given). For patients included with protocol version 5 or higher, if patient reports dialysis at Screening or Cycle 1 Day 1, then renal dialysis is set to 'Yes', otherwise if no dialysis is reported or if information is missing then renal dialysis is set to 'No'.

The time from diagnosis of primary disease to start of study treatment will be calculated in units of years as the difference between the date of start of study treatment and date of diagnosis of primary disease plus 1, divided by 365.25. For the calculation of the time from diagnosis of primary disease to start of study treatment, replacement rules will be applied in case the date of diagnosis of primary disease is incomplete. If day and month are missing, they will be imputed by June 30th to allow for time calculation, if only the day is missing, it will be imputed by 15. If after imputation, the date of diagnosis of primary disease is later than the start date of study treatment, then it will be set to the start date of study treatment.

The time from diagnosis of primary disease to diagnosis of metastatic disease will be calculated in units of years as the difference between the date of occurrence of metastatic disease and date of diagnosis of primary disease plus 1, divided by 365.25. For the calculation of the time from diagnosis of primary disease to diagnosis of metastatic disease, replacement rules will be applied for both dates in case dates are incomplete. If day and month are missing, they will be imputed by June 30th, if only the day is missing, it will be imputed by 15. If after imputation, the date of diagnosis of primary disease is later than the date of diagnosis of metastatic disease, then it will be set to the date of diagnosis of metastatic disease.

Creatinine clearance at baseline will be calculated using the Cockcroft-Gault formula:

$$\text{Creatinine clearance}[\text{mL / min}] = \frac{(140 - \text{age}[\text{years}]) \times \text{weight}[\text{kg}] \times (0.85 \text{ if female or } 1.0 \text{ if male})}{72 \times \text{serum creatinine}[\text{mg / dL}]}$$

A patient will be defined as having renal impairment in case creatinine clearance at baseline is < 30 mL/min.

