4.4.5 Subgroup Analyses

Secondary efficacy endpoints are also analyzed by the following subgroups:

- ECOG Performance status: 0–1 vs. 2
- Presence of CNS metastases at baseline: yes vs. no

- Renal impairment at study entry: yes vs. no
- Creatine clearance at study entry (mL/min): 15-<30 vs 30-<60 vs >=60
- Sex: female vs. male
- HIV status: negative vs. positive
- Patients aged ≥ 65 years: yes vs. no
- Patients aged ≥ 70 years: yes vs. no
- Patients aged ≥ 75 years: yes vs. no
- Patients aged ≥ 80 years: yes vs. no
- Patients aged 65-<75 vs 75-<80 vs ≥ 80
- History of autoimmune disease: yes vs. no
- Progression on, or within 12 months of, prior platinum-based treatment: yes vs. no
- Concomitant steroid treatment ongoing at baseline: yes vs. no
- History of non-urothelial or mixed urinary tract carcinoma histology: yes vs. no
- Tumor location: Ureter vs Renal Pelvis vs all UTUC (Ureter or Renal Pelvis) vs Bladder
- Prior Lines of Treatment for Metastatic Disease (0 vs 1 vs. 2 vs. 3)
- Age-adjusted Charlson comorbidity index (AACI): ≤ 11 vs. > 11
- PD-L1 expression: IC2/3 vs. IC0/1
- PD-L1 expression by IHC Class: IC0 to IC3
- IMvigor211-like patients: yes vs. no
- Region: Australia/Canada/Western Europe vs Eastern Europe vs Other regions

All subgroup analyses are based on the same methods for statistical analyses of the respective secondary efficacy endpoint. Graphical displays such as forest plots are used to visualize the homo-/heterogeneity of secondary efficacy endpoint results across different levels of the subgroups defined above (proportions and 95% CI, or KM medians and corresponding 95% CI as applicable).

The subgroup PD-L1 expression will be derived from the percentage of tumor area infiltrating immune cells as follows:

IC=0 (<1%), IC=1 ($\geq 1\%$ - <5%), IC=2 ($\geq 5\%$ - <10%), IC=3 ($\geq 10\%$).

The subgroup “IMvigor211-like patients” is defined as follows:

Patients with:

- ECOG Performance status: 0–1
- Presence of CNS metastases at baseline: no
- Renal impairment at study entry: no
- Patient with renal dialysis reported at baseline: no
- HIV status: negative
- History of autoimmune disease: no

- Progression on, or within 12 months of, prior platinum-based treatment: yes
- Concomitant steroid treatment ongoing at baseline: no
- History of non-urothelial or mixed urinary tract carcinoma histology: no
- Prior Lines of Treatment for Metastatic Disease: 0 or 1 or 2
- Patients aged ≥ 65 years: indifferent

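### The SAP codes reported baseline dialysis as No for patients included before protocol version 5, so a dialysis patient with clearance of at least 30 mL/min can count as IMvigor211-like; the protocol's dialysis subgroup is also dropped

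*SAP*

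**What the plan says.** **Derivation, SAP 4.3.** Two rules apply, split by protocol version.

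- For the earliest versions the value is fixed in advance. The SAP makes clear that the patient's own record does not matter: the value is No "regardless if any or no dialysis reported or no information given".
- From the fifth version on, the record counts. Dialysis noted at either baseline visit gives Yes, and a blank is treated like an absence: "if no dialysis is reported or if information is missing then renal dialysis is set to 'No".

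No reason is given for the split. SAP 4.7 (Missing Data) covers death dates and CTCAE grades only, and SAP 4.4.4 plans no sensitivity analysis.

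**Use, SAP 4.4.5.** The IMvigor211-like group requires "Patient with renal dialysis reported at baseline: no". It separately requires "Renal impairment at study entry: no", and SAP 4.3 defines that term by clearance alone: "A patient will be defined as having renal impairment in case creatinine clearance at baseline is < 30 mL/min". The group is a subgroup for the secondary efficacy endpoints. It also splits the PD-L1 tables for adverse events, deaths and RECIST-based efficacy, and SAP 4.6.2 repeats the AE overview for it.

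**Protocol 6.6.** Among the subgroups for key safety and/or efficacy parameters is "Patient requiring dialysis: yes vs. no". It appears neither in the efficacy subgroup list of SAP 4.4.5 nor in the safety subgroup list of SAP 4.6.2.

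**The concern.** The flag is named for what was reported at baseline, yet for one block of patients it ignores the report. Where the record says Yes, the analysis variable says No, because of the protocol version under which the patient was included.

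Two things are at stake. First, the IMvigor211-like group is meant to resemble the narrower population of an earlier trial, and absence of dialysis is one of its entry conditions. The override can admit patients whom that condition is meant to exclude. Second, Protocol 1.4 says that the study widens eligibility to clearance of 15 mL/min or more and to patients with past renal failure, so that safety can be described in patients whom earlier trials screened out. A dialysis subgroup serves that aim directly. Renal impairment as the SAP defines it does not replace it, because dialysis plays no part in the definition.

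**Working it through.** The plan gives no figure on this point, so there is none to reproduce. The check runs the rules through every combination and then bounds the effect.

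**Step 1. Who enters the IMvigor211-like group.** The inputs are the dialysis rule and the renal-impairment definition in SAP 4.3, and the group definition in SAP 4.4.5. All other group criteria are assumed met. There are 2 version blocks × 3 dialysis records × 2 clearance bands = 12 combinations. The entry limit of 15 mL/min (Protocol 4.1.1) sets the bottom of the lower band.

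In the 15 to <30 mL/min band, all six combinations are excluded by the renal-impairment criterion, whatever the dialysis flag says. In the ≥30 mL/min band:

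| Version | Dialysis record | SAP flag | In group under SAP | In group if a reported Yes is kept |
|---|---|---|---|---|
| <5 | reported | No | yes | **no** |
| <5 | not reported | No | yes | yes |
| <5 | missing | No | yes | yes |
| ≥5 | reported | Yes | no | no |
| ≥5 | not reported | No | yes | yes |
| ≥5 | missing | No | yes | yes |

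One combination of the 12 places a patient with reported dialysis in the group: version below 5, dialysis reported, clearance of at least 30 mL/min. If missing were also given its own category, the two missing rows would become unclassifiable.

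**Step 2. What clearance of at least 30 mL/min requires.** Solving the Cockcroft-Gault formula in SAP 4.3 for serum creatinine at clearance 30:

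creatinine (mg/dL) = (140 − age) × weight × sex factor / (72 × 30), with sex factor 1.0 for men and 0.85 for women.

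Ages and weights below are assumed for illustration.

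- Man, 65 years, 80 kg: 75 × 80 / 2160 = 2.78
- Woman, 85 years, 60 kg: 55 × 60 × 0.85 / 2160 = 1.30
- Man, 55 years, 100 kg: 85 × 100 / 2160 = 3.94

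A patient with reported dialysis must be at or below such a value to pass the renal-impairment criterion. The same patient must also have ECOG 0–1, no CNS metastases, negative HIV status, no autoimmune history, no baseline steroids, progression during or within 12 months of platinum treatment, purely urothelial histology and at most two prior metastatic lines.

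**Step 3. Bound on the effect.** If k of n patients in the group do not belong there, removing them moves any proportion by at most k/n. This extreme is reached when the k patients are the only ones with the event, or the only ones without it. Neither k nor n is in the documents, so both are assumed. Maximum shift in percentage points:

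| k | n = 300 | n = 500 | n = 700 |
|---|---|---|---|
| 1 | 0.33 | 0.20 | 0.14 |
| 5 | 1.67 | 1.00 | 0.71 |
| 10 | 3.33 | 2.00 | 1.43 |

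**The case against.** The strongest defence is that the override may affect nobody. The SAP wording covers every possible state of the data and does not say that any patient under versions 1 to 4 had dialysis reported. The explicit cut at version 5 may reflect a change in eligibility or data collection, and neither those versions nor the eCRF are available here. This stands as a reason to ask for the count. It does not justify the rule: if the question was not asked before version 5, that would explain a blank but not the overwriting of a recorded Yes. If early entries are thought unreliable, the SAP should say so.

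The renal-impairment criterion is a real safeguard. A reader might infer that dialysis patients from the early versions are in general counted as IMvigor211-like. The documents do not support that: everyone with clearance below 30 mL/min stays out, and the rest must meet every other criterion.

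A reader might also infer that these patients are lost from the safety results, or that a sizeable share of a dialysis subgroup disappears. Neither is supported. They remain in the Safety Population and in all overall TEAE tables, and those with clearance below 30 mL/min appear in the renal-impairment subgroup. No document gives the size of a dialysis subgroup, so no percentage lost can be stated.

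Finally, coding missing as No is defensible for a variable that records whether dialysis was reported, and a separate Unknown level would leave some patients unclassifiable. That part is a preference, not an error.

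**Conclusion.** The point holds in a limited form, as a minor one. The rule for versions below 5 contradicts recorded data without explanation, and it can place a patient with reported dialysis in the IMvigor211-like group when calculated clearance is at least 30 mL/min and every other criterion is met. The omission of the protocol's dialysis subgroup is a separate, unexplained departure that does not follow from the derivation.

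The number of patients affected is not stated and is probably small. Under the assumed 1 to 10 misplaced patients in a group of 300 to 700, the bound on any group proportion runs from 0.14 to 3.33 percentage points. The primary safety estimate, taken in the whole Safety Population, is unaffected.

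**What to change.** 1. In SAP 4.3, set dialysis to Yes whenever it is reported at Screening or Cycle 1 Day 1, under any protocol version.
2. Report how many patients change dialysis class and how many of them leave the IMvigor211-like group. If there is a reason to distrust entries made before version 5, state it beside that count.
3. Restore the dialysis yes/no subgroup from Protocol 6.6 as a patient count with the AE overview.
4. Coding missing as No may stay, with the number of patients lacking dialysis information shown.

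The cost is one derivation line and one small table. The IMvigor211-like outputs need rerunning only if the count in item 2 shows that a patient leaves the group.

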4.4 EFFICACY ANALYSIS

4.4.1 Primary Efficacy Endpoint

Not applicable for this study.

4.4.2 Secondary Efficacy Endpoints

4.4.2.1 Overall Survival

Overall survival (OS) is defined as date of death (due to any cause) or censoring minus date of start of study treatment + 1. Patients who never received treatment are censored with time equal to 1 day.

Date of death is found either in the “Death Attributed to Progressive Disease” form, in the “Study Completion/Early Discontinuation” form (discontinuation date if death) or in the “Adverse Event” form. For patients not known to have died, the date of censoring is based on data from the Survival Follow-Up CRF or on data in the “Study Completion/Early Discontinuation” form:

- “Date of contact” if “Survival status” is “Alive”
- “Date last known to be alive” if “Survival status” is “Lost to Follow-up”
- “Date withdrew consent for survival status” if “Survival status” is “Withdrew consent”.
- Date of study discontinuation in case the patient discontinued the study

The date of censoring will be the maximum of those dates.

In case the patient withdrew consent or is lost to follow-up, but corresponding dates were not entered and only the date of contact is filled in on the Survival follow-up form, then the date of contact will be used instead.

If the date of censoring is still missing, the last date where the patient is known to be still alive (from any CRF page) will be used.

For patients known to have died but whose date of death is missing, the date will be imputed as the last date where the patient is known to be still alive (from any CRF page), but the imputed date will be marked as a death not a censoring.

For patients known to have died but whose date of death is partial, take the latest of the last date where the patient is known to be still alive (from any CRF page) and a completion of the partial date where the missing components are taken as 1 for day and January for month. The imputed date will be marked as a death not a censoring.

Survival status up to the discontinuation date for OS analysis is summarized as number and percentage of patients who

- died
- were still in survival follow-up (still alive)
- discontinued the survival follow-up (e.g., withdrew consent, lost to follow-up, discontinued study).

A Kaplan-Meier (KM) curve for OS is presented including the

- number of patients at risk for death (decreasing over time)
- cumulative number of deceased patients (increasing over time)
- cumulative number of patients censored for OS (increasing over time)

every 6 months.

Two-sided 95% confidence intervals (CIs) for OS probabilities at 6 months timepoints are added to the KM curve. For calculating these CIs:

- KM estimates are transformed to an unrestricted range by the $\log(-\log(x))$ function
- calculation of CIs by applying normal approximation methods to the transformed scaled estimates of the survivor function
- re-transformation of CIs to the original scale.

This approach is triggered by option CONFTYPE=LOGLOG in SAS PROC LIFETEST.

If applicable, median OS is estimated together with a two-sided 95% CI according to the method of Brookmeyer and Crowley 1982.

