### **2.2 SECONDARY OBJECTIVES**

The secondary objectives of the study include evaluation of the efficacy of atezolizumab based on the following disease response endpoints:

- Overall survival (OS), defined as the time from initiation of study treatment to death from any cause
- Progression-free survival (PFS), defined as the time from initiation of study treatment to the first occurrence of disease progression or death from any cause, whichever occurs first. PFS will be calculated based on disease status evaluated by the investigator according to RECIST v1.1, and also by disease status evaluated by the investigator according to modified RECIST
- Overall response rate (ORR), defined as the proportion of patients with a best overall response of either complete response (CR) or partial response (PR). ORR will be calculated based on disease status evaluated by the investigator according to RECIST v1.1, and also by disease status evaluated by the investigator according to modified RECIST
- Disease control rate (DCR), defined as the sum of the CR, PR and stable disease (SD) rates. DCR will be calculated based on disease status evaluated by the investigator according to RECIST v1.1, and also by disease status evaluated by the investigator according to modified RECIST
- Duration of response (DoR), defined as the time from first occurrence of a documented response to disease progression or death from any cause, whichever occurs first. Duration of response will be calculated based on disease status evaluated by the investigator according to RECIST v1.1, and also by disease status evaluated by the investigator according to modified RECIST

Additional secondary study objectives include the evaluation of efficacy of atezolizumab according to the following patient-reported outcomes (PROs; [Appendix 4](#)):

- Change from baseline in health-related quality of life (HRQoL), as assessed using the EORTC Quality-of-Life Questionnaire Core 30 (QLQ-C30)
- EuroQol EQ-5D-5L-assessed utility

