### **Analysis populations**

This study will include the following analysis populations:

- **Safety population**: The primary analysis population for this study will include all enrolled patients who have received at least one dose of atezolizumab. The safety population will be used for all baseline and safety analyses, unless otherwise stated
- **Intent-to-treat population**: The intent-to-treat (ITT) population will include all enrolled patients. The ITT population will be used for all efficacy analyses, unless otherwise stated. In case the difference between the ITT and safety populations is 5 or fewer patients, all efficacy analyses will be based only on the safety population

A per-protocol population will not be defined for this study. However all major deviations (at study entry and on study) will be summarized and reported.

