4.1.5 Intent-to-treat population

The ITT population will include all patients who have signed informed consent and met all eligibility criteria. The ITT population will be used for all efficacy analyses, unless otherwise stated. (According to the Protocol, should the difference between the ITT and safety populations have been 5 or fewer patients – which was not the case –, all efficacy analyses would have been based only on the safety population).

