4.4.2.2 Progression-Free Survival

Progression-free survival (PFS) is determined separately on disease status using RECIST v1.1 and modified RECIST, both evaluated by the investigator.

The date of disease progression is derived based on scan/assessment or death dates, not on visit dates. RECIST assessments/scans contributing towards a particular visit may be performed on different dates.

Progression-Free Survival based per RECIST v1.1 assessments:

PFS is defined as date of first occurrence of tumor progression (earliest of the dates of the RECIST component indicating tumor progression) or date of death (in the absence of tumor progression) by any cause or date of censoring, whichever occurs first, minus date of start of study treatment + 1.

For patients not known to have had a tumor progression or died, the date of censoring is the latest date of assessment from their last evaluable RECIST assessment or the date of start of subsequent cancer therapy whichever occurs first. Patients who never received treatment are censored with time equal to 1 day.

If a patient has no evaluable post-screening RECIST assessments, the patient is censored at the day of study treatment initiation unless the patient dies within 18 weeks. In the latter case, the death date will be used as the date of disease progression.

Progression-Free Survival based per modified RECIST assessments:

PFS according to modified RECIST is defined as:

- date of first occurrence of tumor progression after a modified confirmed response if the patient is a responder according to modified RECIST or
- date of first occurrence of tumor progression in case the patient is not a responder according to modified RECIST or
- date of death (in the absence of tumor progression) by any cause or
- date of censoring, whichever occurs first, minus date of start of study treatment + 1.

For patients not known to have had a tumor progression or died after that modified response, the date of censoring is the latest date of assessment from their last evaluable RECIST assessment or the date of start of subsequent cancer therapy whichever occurs first. Patients who never received treatment are censored with time equal to 1 day.

If a patient has no evaluable post-screening RECIST assessments, the patient is censored with time equal to 1 day unless the patient dies within 18 weeks. In the latter case, the death date will be used as the date of disease progression.

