4.4.2.3 Overall Response

Overall response is determined separately on disease status using RECIST v1.1 and modified RECIST, both evaluated by the investigator.

Best overall response will be derived differently for RECIST assessments and for modified RECIST assessments.

Best overall response based on RECIST v1.1 assessments:

The assessment of best overall response includes post-screening RECIST assessments obtained up to

- disease progression

- death from any cause
- last evaluable RECIST assessment in the absence of disease progression or death
- start of a subsequent anti-cancer therapy

whatever occurs first.

A patient with complete response followed by complete response determined on two consecutive investigator assessments (≥ 4 weeks apart) has confirmed complete response as Best Overall Response.

Otherwise, a patient with complete response followed by partial response or partial response followed by complete response or partial response followed by partial response determined on two consecutive investigator assessments (≥ 4 weeks apart) has confirmed partial response as Best Overall Response.

Otherwise, if there exists at least an assessment of CR, PR or SD, then the patient has Stable disease as Best Overall Response.

If the patient has confirmed complete or partial response, the patient is an overall responder, otherwise, the patient is an overall non-responder. Therefore, if best overall response is Stable Disease, Progressive Disease, Non-Evaluable disease or missing, the patient is an overall non-responder.

Patients who never received treatment are considered as non-responder.

Best overall response based on modified RECIST assessments:

The assessment of best overall response includes post-screening RECIST assessments obtained up to

- death from any cause
- last evaluable RECIST assessment in the absence of death
- start of a subsequent anti-cancer therapy

whatever occurs first.

For best overall response based on modified RECIST, all RECIST assessments are considered even after progression.

The calculations of best overall response based on modified RECIST assessments is similar to the best overall response based on RECIST v1.1 assessments.

In case there are more than one occurrence of CR (or PR in the absence of CR), the first occurrence of CR (respectively PR) will be considered.

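### The OS curve labelled ITT is in practice a treated-patient curve, and the PFS rules conflict for an untreated patient who dies early

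*SAP*

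**What the plan says.** **Population.** Protocol section 6 (Analysis populations) states: "The ITT population will be used for all efficacy analyses, unless otherwise stated". It falls back to the Safety population only if the two differ by 5 or fewer patients. SAP 4.1.5 defines the set: "The ITT population will include all patients who have signed informed consent and met all eligibility criteria". Of the fallback condition it says: "which was not the case". At least 6 ITT patients therefore never received atezolizumab.

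**OS.** Protocol 2.2 gives "Overall survival (OS), defined as the time from initiation of study treatment to death from any cause". The SAP computes OS from the start of treatment and handles patients who have no such date in one unconditional sentence: "Patients who never received treatment are censored with time equal to 1 day".

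**PFS.** SAP 4.4.2.2 repeats that sentence under both RECIST v1.1 and modified RECIST. It also has a rule for patients with no evaluable post-screening assessment. Under modified RECIST, "the patient is censored with time equal to 1 day unless the patient dies within 18 weeks", followed by "In the latter case, the death date will be used as the date of disease progression". The RECIST v1.1 version has the same 18-week exception but censors at the day treatment began.

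**ORR and DCR.** SAP 4.4.2.3: "Patients who never received treatment are considered as non-responder". SAP 4.4.2.5 says the same for disease control.

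**The concern.** The protocol's more-than-5 condition exists so that enrolled but untreated patients are represented in the efficacy results. The SAP says the condition is met, keeps the ITT label, and then applies an OS rule that removes those patients' information. A reader of the report would take ITT OS to include their deaths.

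The rule also sits badly with the rest of SAP 4.4.2.1. There, a patient known to have died whose death date is missing or partial is given an imputed date and counted as a death. Only the untreated patient has a known death turned into a censoring. If the survival-status table in that section is run on ITT, such a patient could appear there as dead and on the curve as censored.

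Under one label, untreated patients count in full in the ORR and DCR denominators and not at all in the OS estimate. SAP 4.4.4 schedules no sensitivity analysis that would expose the difference.

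**Working it through.** **The plan's own figure.** The only design calculation is the Clopper-Pearson table for adverse event rates with N=1000. All nine rows reproduce; for 5 events the limits are 0.16% and 1.16%, a half-width of 0.5%. It has no bearing on this point, and neither document gives a figure for the effect of untreated patients on OS or PFS.

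**Step 1: what day-1 censoring does.** The Kaplan-Meier estimate is S(t) = Π(1 − d_i/n_i) over event times. A patient censored on day 1 is in the risk set only for events on day 1. With no death that day, every d_i and n_i is the same with or without the untreated patients. A check with 1000 simulated treated patients (exponential OS, median 7, 8 or 9 months) plus 6, 20 or 50 untreated gave:
- a difference of 0.0 in estimates and log-log confidence limits at 3, 6, 12 and 24 months, and the same median;
- with one treated death on day 1, a difference below 0.004 percentage points.

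Only the number at risk at time zero and the censored count change.

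**Step 2: size for OS at 6 months.** Inputs:
- Treated median: 8 months, assumed. It is the midpoint of the 7–9 months that Protocol 3.3.6 gives for second-line patients. S = 0.5^(6/8) = 59.5%.
- Untreated patients: at least 6 (SAP 4.1.5). The values 20 and 50 are assumptions that show how the effect grows.
- Untreated median: 3 or 1.5 months, assumed, giving 6-month survival of 0.5^(6/3) = 25% or 0.5^(6/1.5) = 6.25%.

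With u untreated per 1000 ITT patients, the overstatement is (u/1000) × (59.46% − untreated survival). For u = 6: 0.006 × (59.46 − 25) = 0.21 points, and 0.006 × (59.46 − 6.25) = 0.32 points. If all u are dead by 6 months and are added to 1000 treated patients, it is 59.46 × u/(1000+u); for u = 6, 59.46 × 6/1006 = 0.35 points.

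| Untreated | Median 3 months | Median 1.5 months | All dead by 6 months |
|---|---|---|---|
| 6 (documented minimum) | 0.21 | 0.32 | 0.35 |
| 20 (assumed) | 0.69 | 1.06 | 1.17 |
| 50 (assumed) | 1.72 | 2.66 | 2.83 |

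With treated medians of 7 and 9 months the last column at u = 6 is 0.33 and 0.38. In the simulation with 6 untreated patients who all die early, median OS falls by 0 to 0.07 months.

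**Step 3: direction.** The overstatement requires untreated patients to do worse than treated ones. When only half of 50 untreated patients died early and the rest were censored later, 6-month OS still fell (58.8% to 58.4%, median 8 months), but 24-month OS rose (12.3% to 13.5%).

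**Step 4: the PFS rules side by side.** Take an untreated patient who dies in week 10. Under the never-treated sentence the result is censored at day 1. Under the rule for no evaluable post-screening assessment, which this patient also meets on a literal reading, it is an event at the death date. No order of precedence is given. The first reading is easier to apply, because PFS time runs from a treatment start that this patient lacks, but the text does not settle it.

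**The case against.** The time origin comes from the protocol: OS and PFS start at first treatment, and an untreated patient has no such date. The study is single-arm and descriptive, so ITT protects no randomised comparison, and the OS estimate is a sound estimate for treated patients. At the documented minimum the effect is about a tenth of the sampling error: the 95% half-width at 59.5% with 1000 patients is roughly 1.96 × √(0.595 × 0.405/1000) = 3.0 points. Untreated patients are not hidden, because SAP 4.2 reports both population counts and study discontinuations by reason out of ITT. Counting patients without a post-baseline assessment as non-responders follows Protocol 6.5. Moving OS to the Safety population would change almost no number.

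All of this stands as a limit on size. It does not answer the labelling point: a result called ITT should not be numerically the Safety result when the plan has just said that the two sets differ.

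Three stronger readings are tempting, and the documents do not support them:
- **That early deaths vanish from OS and PFS.** Early deaths of treated patients count in full, and for PFS the 18-week rule may make an untreated patient's early death an event.
- **That patients too ill to start treatment died and were removed.** Neither document says that any untreated patient died, or why any went untreated. Eligibility required a life expectancy of at least 12 weeks.
- **That the bias runs to several points.** That needs about 50 untreated patients; only more than 5 is documented.

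**Conclusion.** The point holds for OS as a matter of text and arithmetic. The day-1 rule has no exception for a known death, and it makes the ITT curve the treated-patient curve apart from a negligible tie effect. For PFS the finding is an unresolved conflict between two rules, not a demonstrated loss of events.

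The size is about 0.2 to 0.35 points on 6-month OS at 6 untreated patients. This rests on an assumed 8-month exponential median in treated patients and clearly worse survival in untreated ones. The true number untreated and their deaths are not given, so materiality is unknown, and it is small at the minimum. No hypothesis test depends on it. What is at stake is whether the label describes the estimate, and whether OS, PFS, ORR and DCR can be read together.

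**What to change.** Choose one of two routes.

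1. **Safety population.** Present OS and PFS on treated patients under that name, since both are defined from first dose, and record this as a departure from the protocol's ITT rule. The estimates hardly change. The cost is a sentence in the SAP and revised table titles.
2. **A genuine ITT OS.** For untreated patients, measure from the enrolment date, count known deaths as events, and otherwise censor at the last date known alive. This costs one derivation and mixes two time origins for a few patients. Death ascertainment may also be incomplete: the schedule's survival contacts begin at the treatment discontinuation visit, and before first dose only serious events caused by a protocol-mandated intervention are reported. Consent for follow-up after discontinuation and public records (Protocol 4.6.1) may fill part of the gap. The report should say how many untreated patients have known survival status.

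Under either route, state in SAP 4.4.2.2 which rule prevails for an untreated patient who dies within 18 weeks, for both RECIST versions. Report the number of ITT patients never treated and their known deaths beside the OS results.
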